Critical care admission	 No  Yes, planned from theatre  Yes, unplanned from theatre  Yes, unplanned from ward If yes, CVC inserted?  Yes  No	Critical care bed days	___ days	Postop Hb	 ___ g/L (day 0-1)  ___ g/L (day 1-3)  ___ g/L (day 4-6)  ___ g/L (prior discharge)  Not available	IDA mx (Tick all that apply)	 None  Iron supplementation  TXA  RBC transfusion (if RBC:  1  2  3  4  ≥ 5 units)		
30-day Follow-up									
Cardiovascular complications within 30 days (Tick all that apply)	 None		Bleeding complication within 30 days		 Clinical non-major bleeding  Major bleeding  None				
	 Myocardial infarction  Myocardial injury  Non-fatal cardiac arrest  Coronary revascularisation		Post-operative length of stay		___ days  None				
	 PE (symptomatic non-fatal / asymptomatic)  DVT (proximal / distal; if either symptomatic / asymptomatic)		Highest 30-day complication grade		___  I  II  III  IV  V (if V: Cardiac / PE / noncardiac?)				
			30-day Reoperation		___  Yes ___  No				
			30-day readmission		 No  Yes(planned/unplanned?)				

	 New onset AF  Stroke				If yes: what was grade of complication:  None  I  II  III  IV  V

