2. Critical care bed days (if yes)	Number (days from first post-operative day to day of discharge from critical care. If the patient has not been discharged prior to the end of 30-day follow-up, enter '31').	
3. Postoperative haemoglobin	Not applicable / Available (day 0-1, day 1-3, day 4-6, last prior to discharge) If available, please state value in grams/litre	
4. Postoperative interventions for anaemia	None / iron supplementation / Tranexamic acid / RBC transfusion (If yes: 1, 2, 3, 4, ≥5 units)	
5. Cardiovascular complications within 30 days	None / Myocardial infarction / Myocardial injury / Non-fatal cardiac arrest / Coronary revascularisation / Pulmonary embolism (symptomatic non-fatal / asymptomatic) / Deep venous thrombosis (proximal / distal; if either symptomatic / asymptomatic) / New onset Atrial fibrillation / Stroke (select all that apply) *see Appendix D for definitions Please indicate the POD of the event(s) selected.	• Clinical notes • PACS software
6. Bleeding complications within 30 days	None / Major bleeding / Clinically relevant non-major bleeding *see Appendix D for definitions	
7. Post-operative length of stay	Number (days between from the first post-operative day to day of discharge. If the patient has not been discharged prior to the end of 30-day follow-up, enter '31').	
8. Highest 30-day complication grade	None / Clavien-Dindo Grade I-V (see Appendix D for the full 7-point Clavien-Dindo scale). If grade V, was death cardiac, PE or non-cardiac? (see Appendix D for definitions)	
9. 30-day Reoperation	Yes / No	
10. 30-day Readmission	Yes - planned / Yes- unplanned / No (this applies if patient had died during initial admission) If yes: what is the grade of complication (none, grade I, grade II, grade III, grade IV, grade V)	
11. 30-day postoperative COVID status	None / Preoperative / Postoperative If preoperative: are you still symptomatic (yes/no) and were you vaccinated (no / partial / full)	
12. Haemoglobin on readmission	Not available / Available If available, please state value in grams/litre	
13. Interventions for anaemia at readmission	None / iron supplementation (Oral / Intravenous), blood transfusion (If yes: 1, 2, 3, 4, ≥5 units)	
14. Postoperative outpatient VTE prophylaxis duration	Number (days of pharmacological VTE prophylaxis the patient was discharged home with)	

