- Intra-operative complications are not considered unless they have an adverse effect on the patient post-operatively. The only exception to this is intra-operative death; this is classified as grade V.
- All post-operative adverse events are included, even when there is no direct relationship to the surgery.
- All adverse events within the follow-up period (30 days) are included, even after following discharge.
- Diagnostic procedures are not included. For example, a diagnostic oesophagoduodenoscopy (OGD) to look for a source of bleeding without any intervention would not be considered a complication, but a therapeutic OGD with clipping of a bleeding vessel would be considered a grade IIIa complication. Since negative exploratory laparotomies are considered to be diagnostic procedures, they should not be recorded as complications.

Grade	Definition (examples listed in italics)
I	
Any deviation from the normal postoperative course without the need for pharmacological (other than “allowed therapeutic regimens”), surgical, endoscopic or radiological intervention.
 
Allowed therapeutic regimens are: selected drugs (antiemetics, antipyretics, analgesics, diuretics and electrolyte replacement), physiotherapy and wound infections opened at the bedside but not treated with antibiotics.
 
Examples: Ileus (deviation from the norm); hypokalaemia treated with K; nausea treated with cyclizine; acute kidney injury treated with intravenous fluids.

II	
Requiring pharmacological treatment with drugs beyond those allowed for grade I complications. Blood transfusions and total parenteral nutrition are also included.
 
Examples: Surgical site infection treated with antibiotics; myocardial infarction treated medically; deep venous thrombosis treated with enoxaparin; pneumonia or urinary tract infection treated with antibiotics; blood transfusion for anaemia.

IIIa	
Requiring surgical, endoscopic or radiological intervention, not under general Anaesthetic (GA).
 
Examples: Therapeutic endoscopic therapy (do not include diagnostic procedures); interventional radiology procedures.

IIIb	
Requiring surgical, endoscopic or radiological intervention, under GA.
 
Examples: Return to theatre for any reason.

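### Appendix D gives two different Clavien-Dindo gradings for a negative return to theatre, and the documented form lists five grades for a seven-level scale

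*Protocol*

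**What the plan says.** **Grading rule.** Appendix D, part C, lists considerations before the grade table. One excludes diagnostic procedures and applies this to laparotomy: "Since negative exploratory laparotomies are considered to be diagnostic procedures, they should not be recorded as complications". In the table, grade IIIb is defined as "Requiring surgical, endoscopic or radiological intervention, under GA", and its only example is "Return to theatre for any reason". The IIIa row repeats the exclusion of diagnostic procedures in its example; the IIIb row does not.

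**Recording.** For the highest 30-day grade, the data dictionary (Appendix B, Post-operative Data Fields, item 8) gives the response set as "None / Clavien-Dindo Grade I-V (see Appendix D for the full 7-point Clavien-Dindo scale". Appendix D splits grade III into IIIa and IIIb, and grade IV into IVa and IVb. The Appendix A form, under "Highest 30-day complication grade", offers five boxes without a split: "I II III IV V (if V: Cardiac / PE / noncardiac". The grade at readmission is also listed without a split, on the form and in Appendix B item 10: "If yes: what is the grade of complication (none, grade I, grade II, grade III, grade IV, grade V".

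**Use.** Protocol section 7 makes the 30-day Clavien-Dindo complication rate a secondary outcome and refers to Appendix D for its definition.

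**The concern.** The same event can be recorded in two ways. A collector working from the table ticks grade III; one working from the considerations records nothing for that event. Data come from student-led teams at about 300 anticipated centres, so the outcome relies on one written rule that everybody applies alike. The listed fields offer no later repair: 30-day reoperation is Yes/No only and does not show whether the exploration was negative.

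The second issue is a mismatch between scale and form. Collectors are taught to distinguish IIIa from IIIb and IVa from IVb, and the worked examples in Appendix D assign such grades, yet the documented form has nowhere to enter them.

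**Working it through.** **1. One event, two instructions.** Take a patient returned to theatre under general anaesthetic for an exploration that finds nothing and treats nothing.

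| Instruction in Appendix D, part C | Result for this event |
|---|---|
| Considerations: negative exploratory laparotomy is diagnostic | not recorded |
| Table, IIIb example: any reason for return | IIIb (ticked as III) |
| Table, IIIb definition: an intervention under general anaesthetic | arguable, because nothing was treated |

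The first two lines cannot both be followed.

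**2. Possible size.**

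Inputs:
- N = 6000, from section 9. The plan's figure reproduces: 300 centres × 10 patients per week × 2 weeks = 6000.
- r = share returning to theatre = 5%. Assumption; not in the documents.
- n = share of those returns that are negative = 5% to 15%. Assumption; not in the documents.

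Patients whose grading is in dispute = N × r × n:
- low: 6000 × 0.05 × 0.05 = 15
- high: 6000 × 0.05 × 0.15 = 45

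As a share of the cohort: 15/6000 = 0.25% and 45/6000 = 0.75%.

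This is the largest shift that these rates allow, for two reasons.
- The field records the highest grade. If a share h of these patients has another grade III-V event, the shift in the grade III-or-worse rate is r × n × (1 − h). For the rate of any complication, h is the share with any other graded event, which is at least as large, so that shift is equal or smaller.
- It compares all collectors following one line with all following the other. A mixture lies in between.

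**3. Count of levels.**
- Appendix D: I, II, IIIa, IIIb, IVa and IVb in the table, and V named in the considerations = 7. This agrees with the dictionary's "see Appendix D for the full 7-point Clavien-Dindo scale".
- Appendix A, highest grade: I, II, III, IV, V = 5.
- Readmission grade, Appendices A and B: none plus I, II, III, IV, V = 5 grades.

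The distinctions without an option are IIIa/IIIb and IVa/IVb.

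**The case against.** The best defence of the grading text is its order. Appendix D first says what a complication is, then what is excluded, and the table grades what remains. The IIIb definition requires an intervention, and an example does not normally override an explicit exclusion on the same page. The example may only mean whatever the underlying complication was. This is a fair reading and probably the intended one. But the example admits no exception, no precedence is stated, and the exclusion is repeated in the neighbouring IIIa row and not here. The contradiction in the text stands.

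Collectors must also pass e-learning that includes Clavien-Dindo, with a 100% pass mark (sections 7 and 11). A reader might infer from the contradiction that collectors will in fact grade such events differently. The documents do not show this: the module's content is not given, and it may settle the matter either way.

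On the form, a reader might infer that the a/b split is lost for every grade III and IV patient. The documents do not support that. Appendix A is a summary to be used with the dictionary; section 6 places the full field list in Appendix B and on REDCap; item 8 of the dictionary gives a range and points to all seven levels; and the REDCap options are not shown. Nor does any stated outcome need the split: rates of any complication and of grade III or worse can be computed from five grades. What stands is that the documents disagree, most plainly in the readmission item, where the dictionary itself writes out five unsplit grades.

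**Conclusion.** Wrong as written, as an internal contradiction of minor severity. Appendix D gives two incompatible records for a negative return to theatre, and a named secondary outcome depends on which is used. Under the assumed rates (5% return, 5-15% of these negative) the effect is at most about 0.25-0.75 percentage points on the grade III-or-worse rate, or 15-45 of 6000 patients. It is a ceiling for those assumed rates and should not be read as an estimate of bias; other rates scale it in proportion.

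The five-against-seven mismatch is also real, but the supported conclusion is limited: as documented, the a/b split may not be captured. The primary outcome, compliance with the audit standards, is untouched by either issue.

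**What to change.** 1. Align the grade IIIb example with the protocol's own rule on diagnostic procedures, for instance: *Therapeutic return to theatre under GA; a negative exploration is not graded.* Check that the Clavien-Dindo e-learning module says the same.
2. Give I, II, IIIa, IIIb, IVa, IVb and V as the options for both the highest 30-day grade and the readmission grade, on the Appendix A form, in the Appendix B dictionary and in REDCap. If REDCap already holds seven levels, only the two appendices need changing.

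The cost is one example line and two extra options on each of the two grade items. No clinical care or follow-up changes.

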Appendix E: Steps for successful inclusion of your centre

1. Contact your local lead about participation in the CASCADE study. They will connect you to any other interested medical students and foundation doctors.
2. Form a mini-team of up to three collaborators. A medical student should be co-ordinating the team and leading audit registration and data collection. The student should be supported by at least one motivated doctor. This can be any doctor from junior doctor to consultant grade. The collaborating doctor could be:
 - A junior (e.g. FY1, FY2, CT1, CT2) you know on rotation in the surgical department.
 - If you don't know any juniors working in the surgical teams, try walking onto the ward to find an FY1 to ask who the best FY1/2 to help the audit is; this approach often succeeds. If there is an FY1/2 on an academic rotation, they may be well placed to help you.
 - The consultant who will be supervising your surgical placement.
 - The consultant lead for audit in the department of surgery.
 - A member of your local registrar-led research collaborative (<http://www.asit.org/resources/collaboratives>).
3. Up to four teams of students can cover consecutive 2-week periods, working together to deliver 30-day follow-up. Discuss with your regional lead to establish a 14-day consecutive data collection period from below to suit your availability:
 - Period 1: 00:00 24th Jan 2022 - 23:59 06th Feb 2022 (+ 30 Day Follow-up)
 - Period 2: 00:00 07th Feb 2022 - 23:59 20th Feb 2022 (+ 30 Day Follow-up)
 - Period 3: 00:00 21st Feb 2022 - 23:59 06th Mar 2022 (+ 30 Day Follow-up).
 - Period 4: 00:00 07th Mar 2022 - 23:59 20th Mar 2022 (+ 30 Day Follow-up).
 - Period 5: 00:00 21st Mar 2022 - 23:59 03rd Apr 2022 (+ 30 Day Follow-up).
4. Ensure that you secure formal audit approval from your hospital's clinical audit department prior to commencing data collection. This may seem daunting at first but is in fact quite straight forward. Every hospital has an audit department and it is a simple case of approaching them with the information we have prepared in this protocol and applying this to the local audit registration form. You will need a local consultant to support you and sign the hospital's audit form (this should be the same consultant which is supervising the mini-teams). Ensure that the audit department know that this is part of a national project and that you will enter data on REDCap.

*It is essential that you begin this process **immediately**; approval can take up to a month or more. You may have to contact or even visit the hospital before your placement starts to ensure that you will be ready. If you have any difficulties contact your regional lead, your supervising junior doctor/consultant or the steering committee.*

5. Contact your hospital's Caldicott Guardian (often the medical director - the audit department can help you find out who this is) to request permission to submit data to REDCap. You need additional permission from the Caldicott Guardian to store any patient numbers on REDCap.
6. Agree with your audit office and Caldicott Guardian how you will facilitate 30-day follow-up. You will require the hospital number for each patient to undertake follow-up, and so this needs to be stored in a safe and secure manner until accessed for 30-day follow-up, in line with local and national data governance guidance. This can be within the hospital site (paper or computer), or on REDCap (if permission from the Caldicott Guardian has been obtained).
7. Once the audit is registered and you have Caldicott Guardian approval, please forward evidence of this to your regional lead. REDCap accounts will not be issued until proof of audit registration AND Caldicott approval has been received.
8. Arrange to meet with the other members of your mini-team, including the junior doctor and, if possible, supervising consultant. If possible, it is also highly recommended to meet with the preceding mini-team at your centre (this would ideally include **a period of shadowing**):
 - They will have a lot of helpful advice regarding what worked well. In your mini-team, agree in advance who will be responsible for each stage of the project (e.g. identifying patients, collecting baseline data, completing follow-up, data entry to REDCap).
 - Talk through how you will identify patients and collect required data, it will be particularly helpful if the consultant is present to offer guidance regarding this. Agree who will access blood test results; will students have a login or will the junior doctor check the results?
9. Identify all patients fitting the inclusion criteria within your specified two-week window. Contact your regional lead with any questions or issues that may arise over your data collection period.
10. Regularly follow-up for information on complications over the 30-day post-operative period. This study is prospective, so you should not wait until the end of the post-operative period to

follow-up patients (this would be retrospective). Discuss the best way to follow up patients with the consultant supervising your audit, as this will vary from centre to centre.

Be proactive in identifying post-operative adverse events, as this will prevent under-estimation of true complication rates. Remember that in this audit no changes to normal patient follow-up should be made.

Strategies for identifying complications in the follow-up period include:

- *Regularly reviewing patient notes to identify in-hospital complications.*
- *Reviewing clinic notes and clinic letters, if seen in clinic by 30 days.*
- *Checking electronic systems and handover lists for re-admissions.*
- *Checking for A&E re-attendances.*

If case notes are reviewed shortly prior to discharge they do not need to be requested/retrieved again for follow-up at 30-days, but do check electronic records for discharge letters, clinic letters, re-admissions.

11. Ensure all data has been uploaded to the REDCap system by the data collection deadline, and you have completed all fields, avoiding missing data points. If more than 5% of patients at your centre have missing data, your centre cannot be included in the CASCADE dataset and your name will be withdrawn from the author list.
12. It is a condition of participation in CASCADE that following completion of the audit at your centre you must ensure that your local results are presented to your hospital's surgical department and/or reported back to the audit department. You may also like to return to present again at a later date, when the final national results of CASCADE become available.

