
1. Early recognition of patients needing specialist postoperative input
	
Royal College of Anaesthetists: Guidelines for the Provision of Anaesthesia Services 2019²⁵
 
 • Provision of Postoperative Care Recommendation 3.23: Mechanisms for the early recognition of patients requiring specialist postoperative input from geriatrician-led services and/or critical care should be developed. These should include patients at risk of or presenting with delirium, multiple medical complications, functional decline or complex discharge planning.

2. Postoperative intravenous iron therapy is indicated in patients with iron deficiency anaemia
	
International consensus statement on Postoperative Anaemia after Major Surgery 2018²⁶
 
 • Postoperative iron therapy: Should postoperative iron therapy be indicated, i.v. formulations are recommended

3. Extended pharmacological VTE prophylaxis is indicated in patients at high VTE risk after major abdominal or pelvic surgery
	
National Institute of Clinical Excellence: Venous thromboembolism in over 16s: reducing the risk of hospital-acquired deep vein thrombosis or pulmonary embolism (NG89) 2018
 
 • Consider extending pharmacological VTE prophylaxis to 28 days postoperatively for people who have had major cancer surgery in the abdomen.

Methods

1. Summary

A prospective, multicentre, study will be delivered by STARSurg Collaborative & EuroSurg Collaborative across Europe. Mini-teams of up to four collaborators (medical students and at least one doctor) per speciality group per data collection period will prospectively collect data over a continuous 14-day period at each participating centre. This will be on consecutive patients undergoing major abdominal surgery, with follow-up to 30 postoperative days. All mini-teams should be supervised by a consultant in surgery.

2. Study Aims:

- **Primary Aim:** To audit compliance to pre-, intra-, and postoperative audit standards in reducing risk of postoperative cardiovascular complication.

- **Secondary Aims**
 - To characterise rates and risk factors associated with postoperative cardiovascular complications following major abdominal surgery in Europe.
 - To explore the association of pre-operative and postoperative anaemia with postoperative cardiovascular complications and short-term outcomes (length of stay, readmission and 30-day mortality).

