- 30-day reoperation rates
- Critical care bed days up to 30 days postoperatively
- Length of in-patient stay (days) up to 30 days postoperatively
- 30-day readmission rates
- 30-day bleeding event rates (see **Appendix D: Definitions of Key Outcomes**)
- Length of pharmacological VTE prophylaxis (days) up to 30 days postoperatively.

Follow-up should be performed in line with current routine practice within each hospital settings. No additional telephone, in-person or questionnaire-based follow-up is required. Source data may be acquired from hospital in-patient notes, clinical electronic systems, or outpatient letters.

Prior to collecting data, all collaborators will be required complete the mandatory e-learning modules available from the CASCADE project online hub:
<https://incept.ac.uk/course/view.php?id=7>

These include: (1) CASCADE Patient selection; (2) Clavien-Dindo classification (3) Postoperative cardiovascular complications; (4) Postoperative bleeding complications; (5) VTE pharmacological prophylaxis; (6) Data safety governance; (7) Quiz

8. Data Governance:

Data will be collected and stored online through a secure server running the Research Electronic Data Capture (REDCap) web application,^{27,28} and allows safe anonymised data storage by collaborators across Europe. The service is managed by the Birmingham Surgical Trials Consortium (BiSTC) REDCap system hosted at the University of Birmingham, United Kingdom. The security of the study database system is governed by the policies of the University of

Birmingham. Data management and data security within the BiSTC REDCap will abide by the requirements of the General Data Protection Regulations (GDPR) and any subsequent amendments. Collaborators will be given secure REDCap project server login details, allowing secure data storage on the REDCap system.

No patient data will be uploaded or stored on the REDCap database without prior local permissions. All data should be handled in accordance with local data governance policies, and all paper copies of any data should be destroyed as confidential waste within the centre once uploaded to REDCap. Data collected during the CASCADE study can be used for future analyses at the Study Management Group's discretion.

9. Data Analysis & Sample Size:

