REDCap accounts will not be issued until evidence is sent to your university's regional lead that the following approvals are in place at your centre:

- *Successful registration of CASCADE with the audit department.*
- *Caldicott Guardian permission for data to be submitted to REDCap.*

11. Quality assurance:

Design: This protocol was written with guidance from an expert cross-speciality advisory group.

Training: CASCADE Regional Leads are encouraged to hold local meetings with collaborating teams at their medical school to brief them on the protocol, and to feedback any local issues or questions raised. To ensure collaborators understand the study topic, inclusion criteria, primary outcomes, application of the Clavien-Dindo classification and the principles of data governance, they will all be asked to complete online **e-learning** on these (pass mark is 100%) prior to starting data collection (online at: <https://incept.ac.uk/course/view.php?id=7>).

Project team structure: Medical students will take the lead in disseminating and delivering this study alongside junior doctors. These 'mini-teams' should be supervised by up to two consultants (two surgeons or anaesthetists) at each site in the UK & Ireland, and by a consultant per surgical specialty in the rest of Europe (**Figure 1**). Each team should include at least one qualified doctor to provide additional local support for participating medical students.

[figure not shown]

Figure 1: STARSurg “Mini-team” structure, roles, and responsibilities.

Data completeness: Following data collection, only data sets with >95% data completeness will be accepted for pooled national analysis. To emphasise the importance of data completeness to collaborators, data collection periods with >5% missing data points will be excluded from the study and collaborators from those periods withdrawn from the published list of citable collaborators.

Validation: This methodology for student-driven snapshot audit has been widely validated across multiple datasets, both nationally in the UK and Ireland and internationally, demonstrating high levels of case ascertainment (typically greater than 90 to 95%) and data accuracy (greater than 96 to 98%).^{29,30}

12. Authorship:

In accordance with National Research Collaborative (NRC) authorship guidelines³, all research outputs from CASCADE will be listed under a single corporate authorship (“STARSurg Collaborative & EuroSurg Collaborative”).

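### The 30-day secondary outcomes cannot separate patients observed event-free to day 30 from patients with no record after discharge, so post-discharge events are open to an undercount of unknown size

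*Protocol*

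**What the plan says.** Methods section 7 lists as secondary outcomes the 30-day incidence of cardiovascular complications and the 30-day rates of complications by Clavien-Dindo grade, reoperation, readmission and bleeding. Section 2 adds an aim on anaemia and "short-term outcomes (length of stay, readmission and 30-day mortality". The Clavien-Dindo notes in Appendix D make the window explicit: "All adverse events within the follow-up period (30 days) are included, even after following discharge".

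Follow-up is by routine care. Section 7 says "No additional telephone, in-person or questionnaire-based follow-up is required" and, on where the data come from, "Source data may be acquired from hospital in-patient notes, clinical electronic systems, or outpatient letters". Appendix E step 6 says "You will require the hospital number for each patient to undertake follow-up". Step 10 lists notes, clinic letters, electronic systems, handover lists and A&E re-attendances, then says "If case notes are reviewed shortly prior to discharge they do not need to be requested/retrieved again for follow-up at 30-days". The sentence does not end there; its second half keeps an electronic check in place: "but do check electronic records for discharge letters, clinic letters, re-admissions".

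Appendix B, which section 6 calls the full list of fields (also on REDCap), gives these post-operative items: 5 (cardiovascular complications), 6 (bleeding), 8 (highest complication grade), 9 (reoperation) and 10 (readmission). Each allows an event or None/No. Death appears only as a grade V complication.

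Two rules penalise missing data. Under section 11, "data collection periods with >5% missing data points will be excluded from the study". Appendix E step 11 instead excludes a centre if more than 5% of its patients have missing data.

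**The concern.** The outcome is defined over 30 days in and out of hospital, but after discharge the observation depends on what the reviewed records show. The form does not keep the two apart. A patient known to be well at day 30 and a patient with no trace after leaving hospital on day 3 get the same code.

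The Introduction offers the cardiovascular rates as benchmarks for future randomised trials. For part of the cohort they may be in-hospital rates carrying a 30-day label. Late venous thromboembolism, bleeding, readmission and death after discharge are most exposed. In-hospital events, length of stay and critical care days are little affected. The aim on extended thromboprophylaxis is also exposed, because item 14 measures the days of prophylaxis a patient was sent home with, and the events that bear on it fall largely after discharge.

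**Working it through.** **1. What the form allows.** Items 5, 6, 8, 9 and 10 have no answer for an unknown status. The haemoglobin fields at transfusion (intra-operative item 12) and at readmission (post-operative item 12) do offer one, so the form allows for unavailable data there but not for the 30-day outcomes. No field holds a date of last contact, the sources checked, or whether day 30 was reached. The postoperative day under item 5 is requested only for patients with an event. An unseen patient can therefore only be coded None/No or left blank.

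**2. What a blank costs.** Inputs from sections 1 and 9: 300 centres, 10 patients a week, 14 days.

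- Sample: 300 × 10 × 2 = 6000, which reproduces the protocol's figure.
- Per centre: 10 × 2 = 20 patients over one period.
- Appendix E step 11 (patients): 1/20 = 5% is not above the limit; 2/20 = 10% is. Two patients with a blank exclude the centre.
- Section 11 (data points): Appendix B has 23 + 12 + 15 = 50 numbered items. Leaving all five outcome items blank loses 5/50 = 10% of a patient's items, so more than half of patients (5%/10%) would need all five blank to pass 5%.

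The two rules use different units and give very different incentives. The pressure towards None/No comes from step 11, hardly from section 11.

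**3. Possible size (illustration only).** Let f be the share of 30-day events arising after discharge and m the share of those that never reach the records reviewed. Then

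recorded rate = true rate × (1 − f × m).

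The protocol gives neither f nor m. Assumed: f 20-50%, m 10-50%. The relative undercount f × m then runs from 0.2 × 0.1 = 2% to 0.5 × 0.5 = 25%. For comparison, the 95% half-width is 1.96 × √(p(1 − p)/6000), ignoring clustering by centre. The 25% rate is the upper figure in the Introduction; the other rates are assumed.

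| True rate | Half-width (points) | Recorded rate | Events missed | Share of events missed at which bias equals half-width |
|---|---|---|---|---|
| 2% | 0.35 | 1.96% to 1.5% | 2 to 30 | 17.7% |
| 5% | 0.55 | 4.9% to 3.75% | 6 to 75 | 11% |
| 10% | 0.76 | 9.8% to 7.5% | 12 to 150 | 7.6% |
| 25% | 1.10 | 24.5% to 18.75% | 30 to 375 | 4.4% |

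For common outcomes, much of the assumed range is bias larger than sampling error. For a 2% outcome it mostly lies within it. One pair of f and m will not suit every outcome.

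**4. What can already be recovered.** Item 5 (postoperative day) and item 7 (length of stay) together separate in-hospital from post-discharge cardiovascular and thromboembolic events that were found. There is no such timing for bleeding, complication grade or reoperation. Neither item identifies patients in whom a post-discharge event could not have been seen.

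**The case against.** The best defence is that record-based follow-up is a deliberate limit of an audit that must not alter care, and that the protocol guards against under-recording. Step 10 tells teams to look actively and regularly, and names clinic letters, readmissions and A&E attendances. Four stronger readings are tempting, and the documents do not support them.

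- *Review before discharge is enough.* It is not: the waiver covers re-retrieving case notes only, and the same sentence still requires the electronic check. What stands is that the check has no date.
- *Only the operating hospital's records are used.* Tracing by hospital number suggests this, but section 7 does not limit electronic systems or letters to one hospital, and shared systems may show outside events. How far they reach is not stated.
- *The error is differential and distorts the thromboprophylaxis comparison.* If 90% of events were found with extended prophylaxis and 70% without, equal true risks would give a ratio of 0.9/0.7 = 1.29. Both percentages are invented for the example, and nothing in the protocol fixes even the direction: cancer patients may be seen more often in clinic, yet those treated at a referral centre may return elsewhere.
- *The penalty in section 11 drives teams to enter None.* As counted above, that rule bites weakly.

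It is also fair that denominators and censoring belong in an analysis plan, which is not shown. But no analysis plan can recover a distinction the form never collected. The case ascertainment and data accuracy quoted in section 11 do not settle the matter either: the first concerns finding eligible patients, and the text does not say that the second tested capture of post-discharge events.

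**Conclusion.** The concern holds as a data-collection gap in the secondary outcomes. Outcomes defined to day 30 are taken from routine records on a form that codes an unobserved patient as a non-event, or as a blank that Appendix E step 11 penalises. That teams will choose None/No over a blank is an inference, but the form leaves no other compliant entry. Missed events push the recorded rates down.

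The size cannot be derived from the protocol. The 2-25% relative undercount depends wholly on the assumed f and m and should be cited only as an illustration. A differential effect on the thromboprophylaxis aim is possible but not shown. The primary outcome, compliance with audit standards, does not depend on these event fields and is largely unaffected.

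**What to change.** 1. Add to Appendix B and REDCap the date and the source of the last record reviewed. State in advance what counts as ascertained to day 30, since a system searched with nothing found is not the same as a patient seen.
2. Add *not ascertained after discharge* to items 5, 6, 8, 9 and 10, and exempt it from the missing-data rules.
3. Reconcile section 11 (data points per period) with Appendix E step 11 (patients per centre), so that one unit applies.
4. Require the electronic check already asked for in step 10 to be made on or after day 30 for every patient.
5. Keep whole-cohort 30-day rates, labelled as record-based. Beside them give in-hospital rates and the share of patients ascertained to day 30. For bleeding, grade and reoperation, in-hospital rates also need a before/after-discharge marker.
6. Add a sensitivity analysis that varies the post-discharge event rate in patients not ascertained, with zero (the recorded rate) as the lower end.

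Do not restrict the denominator to ascertained patients or censor at the last record. Having a late record depends partly on having had an event, so either would bias the rates upward.

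The cost is two extra REDCap fields, an added answer option, the timing marker if in-hospital rates are wanted for every outcome, and a less favourable statement of follow-up completeness. No patient contact is added.
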